#### 4. Study Objectives

The primary objective of this study is to demonstrate the safety and effectiveness of the Harmony™ TPV system as measured by freedom from procedure or device-related mortality at 30 days and percentage of subjects with acceptable hemodynamic function at 6 months.

#### 5. Investigation Plan

This is a prospective, non-randomized, multi-center study, with each center following a common protocol. Up to 40 subjects will be implanted at up to 15 centers in the United States, Canada, and Japan. It is anticipated that more than 40 subjects will be enrolled (i.e. consented) to meet the target of up to 40 implants as not all subjects will be suitable for implantation. No site shall implant more than 10 subjects., excluding roll-in subjects. Subjects who discontinue participation prematurely following implant will be included in the analysis of results (as appropriate) and will not be replaced in the enrollment of total study subjects implanted. All implanted subjects will receive the Harmony™ TPV, either size 22 or 25. Each implanted subject will be followed for five years or until the subject's Harmony™ TPV is explanted. Subjects who failed the first screen for the TPV 22 device before the second device size TPV 25 were introduced, will either exit from the study or rescreen for the second device size later when TPV 25 device is available. All subjects who are rescreening for the new valve size TPV 25 will have all baseline assessments performed for TPV 25.

The addition of the second device size (Harmony TPV 25) is intended to expand the number of patients anatomically suitable for implantation and will include a Roll-In cohort of Harmony TPV 25 subjects. A minimum of five and up to eight qualifying subjects will be implanted with the Harmony™ TPV 25 at up to four Study Proctor sites. Each Study Proctor site can implant up to three subjects. The Roll-In phase is described in Section 8.4 Harmony TPV 25 Roll-In Phase in Clinical Investigation Plant (CIP) version 6. If Roll-in phase outcome measures are met and no concerns are raised by the DMC, Steering Committee or Medtronic, the Harmony™ TPV 25 will be made available to all participating Harmony™ TPV study sites. All subjects in Roll-In phase and all subjects after Roll-In phase will be included in the 40-subject analysis cohort. Following the completion of the 40 pivotal cohort of the TPV 22 and TPV 25, the TPV 25 was modified and is referred to as modified TPV 25 (mTPV 25). There will be an added cohort of up to 15 subjects implanted with the mTPV 25. This additional cohort will include 10 US implants and up to 5 OUS implants from Canada and/or Japan. The mTPV 25 cohort is described in Section 8.5. Addition of mTPV 25 Cohort in CIP version 6.The following measures will be implemented to minimize risks to the study subjects:

• All subjects will be acceptable surgical candidates

Page 9 of 24

Form

Medtronic

Revision 5.1

- Implanting physicians will have considerable experience in interventional congenital cardiology procedures
- Investigative sites will have comprehensive congenital cardiology and surgery programs, with established capacity for emergency catheterization and cardiovascular surgery should it become necessary
- Patients being considered for the study will be rigorously screened
- Subjects will undergo thorough assessments during their pre-implant workup
- Subjects will be rigorously followed over the course of the study. The follow-up protocol
  includes frequent contact with the investigative clinicians, echocardiography, magnetic
  resonance imaging and radiography. Collectively, the follow-up protocol will enable detection of
  deterioration in TPV function should it occur, and allow appropriate intervention, as adjudicated
  by the implanting physician
- Radiation dosages will be monitored and documented for the implant procedure and for each radiography and CT angiography procedure. If the Substantial Radiation Dose Level (SRDL) of 500 Gy\*cm² is met for any given procedure, the subject will be educated about examining the tissue site for a possible skin reaction within 30 days and clinical follow-up will be required.
- Any unanticipated or unforeseen complications will be reported to the Institutional Review Board (IRB)/Ethics Committee (EC), to the appropriate regulatory agencies, and to Medtronic
- An independent Data Monitoring Committee (DMC) will review adverse events and interim
  results in order to advise Medtronic regarding study conduct, should safety concerns be
  identified

#### **Inclusion Criteria**

- Subject has pulmonary regurgitation as per one or more of the following criteria:
  - Severe pulmonary regurgitation as measured by Doppler echocardiography, or
  - Pulmonary regurgitant fraction ≥ 30% as measured by cardiac magnetic resonance imaging
- Clinical indication for surgical placement of a RV-PA conduit or prosthetic pulmonary valve per one or more of the following criteria:
  - Subject is symptomatic secondary to pulmonary insufficiency (e.g. exercise intolerance, fluid overload) as classified by the investigator, or
  - Right ventricular end diastolic volume index (RVEDVi)  $\geq$  150 ml/m^2, or
  - Subject has RVEDV: LVEDV Ratio ≥ 2.0

#### **Exclusion Criteria**

- Anatomy unable to accommodate a 25 Fr delivery system
- Obstruction of the central veins
- Clinical or biological signs of infection including active endocarditis
- Planned concomitant procedure at time of Harmony™ TPV implant
- Positive pregnancy test at baseline (prior to CT angiography and again prior to implant procedure) in female subjects of child bearing potential

Revision 5.1 Page 10 of 24

Form

Medtronic

- Patients with right ventricular outflow tract obstruction (RVOTO) lesions surgically treated with a RV- PA conduit implant
- A major or progressive non-cardiac disease (e.g. liver failure, renal failure, cancer) that results in a life expectancy of less than one year
- Planned implantation of the Harmony™ TPV in the left heart
- RVOT anatomy or morphology that is unfavorable for device anchoring
- Known allergy to aspirin, heparin, or nickel
- Echocardiographic evidence of intracardiac mass, thrombus, or vegetation
- Pre-existing prosthetic heart valve or prosthetic ring in any position

While the primary safety endpoint is measured at 30 days, primary objective analysis will be completed upon completion of the primary efficacy endpoint, which is measured at 6 months. Therefore, the analysis for primary objectives will be performed when all subjects have reached their 6 month endpoints.

Final analysis on the additional outcome measures will be performed when the implanted subjects have reached their 5year endpoints, with the exception of the following endpoints, which will be analyzed in conjunction with the primary objective analysis (when all implanted subjects have reached their 6-month visit):

- Technical success at exit from catheterization lab/operating room (OR)
- Procedural success at 30 days

#### 6. Determination of Sample Size

There is no sample size calculation for the primary objectives. The primary analysis will include 40 pivotal cohort of the TPV 22 and TPV 25. For the modified TPV 25 (mTPV 25), an additional cohort of up to 15 subjects implanted with the mTPV 25 (10 US implants and up to 5 OUS implants from Canada and/or Japan).

The pooled analysis cohort will include data from this study in addition to the data from the Native Outflow Tract Transcatheter Pulmonary Valve Research Clinical Study (IDE #G120175, n=20).

#### 7. Statistical Methods

#### 7.1 Study Subjects

#### 7.1.1 Disposition of Subjects

[figure not shown]
The CONSORT flow diagram will be used to summarize the disposition of enrolled subjects. In the enrollment process, subjects who failed screening for TPV 22 were rescreened when the TPV 25 became available. The subjects re-screened for TPV25 were assigned the same subject ID plus the letter B

Revision 5.1

Page 11 of 24

If the subject was re-screened for mTPV 25 when the mTPV25 became available, the subject was given M plus the subject ID. The flowchart below displays the process of rescreening for subjects initially screened for TPV 22. The baseline data collected during the most recent screening process will be used for all analysis.

#### 7.1.2 Clinical Investigation Plan (CIP) Deviations

A protocol deviation is defined as an event where the clinical investigator or site personnel did not conduct the study according to the protocol or the Investigator Agreement. Examples of protocol deviations include but are not limited to the following:

- Failure to obtain informed consent prior to participation
- Incorrect version of the informed consent form used
- Failure to obtain IRB/EC approval before the start of the study

Page 12 of 24 Medtronic

**Form** 

Revision 5.1

vision 5.1

- Enrolled subject did not meet inclusion/exclusion criteria
- Required testing and/or measurements not done or incorrectly done
- Subject does not attend follow-up visit or follow-up visit outside window
- Unauthorized use of investigational devices
- Adverse events not reported in the required time frame as required by regulation or as specified in the CIP
- Control of study devices not maintained
- Source data permanently lost
- Enrollment of patients during lapse of IRB/EC approval

The number of subjects with protocol deviations and the number of protocol deviations will be summarized by type of deviation.

#### 7.1.3 Analysis Sets

The analysis subsets are defined as follows

#### **Enrolled Cohort**

The enrolled cohort consists of all enrolled subjects. Subjects are considered enrolled at the point of signing the Informed Consent Form.

#### **Catheterized Cohort**

The catheterized cohort consists of all subjects who undergo catheterization for possible implantation of the Harmony™ TPV.

#### **Attempted Implant Cohort**

The attempted implant cohort consists of all subjects who undergo catheterization and a Harmony™ TPV implantation was attempted (Harmony™ TPV is introduced into the subject's body).

#### **Implanted Cohort**

The implanted cohort consists of all subjects who undergo catheterization and a Harmony™ TPV was implanted.

#### Implanted > 24 hours Cohort

\_

<sup>1 Subjects must meet all inclusion/exclusion criteria to be eligible for implantation. However, it will not be considered a protocol deviation if study related testing (e.g., echo, CT cardiac angiography, or Screening Committee assessment) of a consented subject identifies implantation eligibility criteria that are not met.

Revision 5.1

Page 13 of 24

The implanted >24 hours cohort consists of all subjects who have a Harmony™ TPV implanted which remains implanted for greater than 24 hours.

#### 7.2 General Methodology

Descriptive statistics will be used to report patient population characteristics, operative, and postoperative data. Continuous variables will be summarized with means, standard deviations (SD), medians, first and third quartiles, minimums, and maximums. Categorical variables will be summarized with frequencies and percentages.

#### 7.3 Center Pooling

No poolability analyses are planned. Comparison among centers or any particular groups will only be conducted per request by Food and Drug Administration (FDA).

#### 7.4 Handling of Missing, Unused, and Spurious Data and Dropouts

Every effort will be undertaken to minimize missing data. In time-to-event outcomes drop-outs will be censored at the time of discontinuation, consistent with the Kaplan-Meier approach.

Unless otherwise specified in each objective, no statistical techniques will be used to impute missing data for continuous or categorical outcomes. If a subject's data are missing for any reason, that subject will not be included in that portion of the analysis. The number of subjects included in each analysis will be reported so that the reader can assess the potential impact of missing data.

In the case of partial dates, if only the month and year are known, the event or assessment will be analyzed as if it occurred on the 15th of that month. If only the year is known, the event or assessment will be analyzed as if it occurred on June 30th of that year. These resolutions of partial dates are subject to the restrictions that pre-procedure assessments must occur between the enrollment date and the procedure date or within the window defined in the CIP. The post-procedure events and assessments must occur no earlier than the procedure date. According to the section 6.1 of the CIP, the windows for pre-procedure assessments are:

- CMR exam (functional): within 52 weeks prior to the implant date
- Clinical evaluation: within 24 weeks prior to the implant date

## 7.5 Adjustments for Multiple Comparisons

[figure not shown]
No adjustments will be made for multiple comparisons.

## 7.6 Demographic and Other Baseline Characteristics

The analysis of baseline characteristics will be descriptive in nature. Summary statistics will be provided for baseline demographic and clinical variables for the enrolled cohort and catheterized cohort as defined in section 7.1.3, respectively.

Revision 5.1

Page 14 of 24

#### 7.7 Treatment Characteristics

The analysis of procedure characteristics and concomitant procedures will be descriptive in nature. Summary statistics will be provided as appropriate.

#### 7.8 Interim and Supplemental Analyses

#### 7.8.1 Interim Analysis for TPV 25 Roll-in Cohort

The procedural feasibility, and hemodynamic performance and safety profile at hospital discharge following Harmony TPV 25 implantation of the Roll-In cohort will be analyzed. The outcome measures are defined as:

#### **Procedural Feasibility:**

- No device- or procedural-related mortality, with
- successful access, delivery and removal of the delivery system, and
- deployment and correct positioning (including minor repositioning if needed) of the device.

#### **Hemodynamic Performance:**

Mean RVOT gradient ≤ 40mmHg as measured by echocardiography

#### **Safety Profile:**

None of the following device- or procedure-related serious adverse events:

- Life-threatening major bleed
- Major vascular or cardiac structural complications required unplanned reintervention or surgery
- Pulmonary embolism

#### 7.8.2 Supplemental Analysis for mTPV 25 Cohort

The procedural feasibility, hemodynamic performance, and safety profile of mTPV 25 at 1 month following mTPV 25 implantation will be analyzed. The outcome measures are defined as:

#### **Procedural Feasibility:**

- No device- or procedural-related mortality, with
- successful access, delivery and removal of the delivery system, and
- deployment and correct positioning (including minor repositioning if needed) of the device.

#### **Hemodynamic Performance:**

[figure not shown]
Mean RVOT gradient ≤ 40mmHg as measured by echocardiography

#### **Safety Profile:**

None of the following device- or procedure-related serious adverse events:

Life-threatening major bleed

Revision 5.1

Page 15 of 24

- Major vascular or cardiac structural complications required unplanned reintervention or surgery
- Pulmonary embolism

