## 8. Study Procedures

### 8.1. Schedule of Events

Evaluation / Visit	Pre-Implant	Implant 	Discharge	1 Month	6 Months	1 Year	Annual (2-5 Years)
Visit Window	Within 24 weeks prior to Implant procedure unless otherwise specified	Implant procedure date	Prior to hospital discharge, or at 30 days post-implant if subject remains hospitalized	Between 2 and 6 weeks after implant	Between 23 and 29 weeks after implant date	Between 44 and 60 weeks after implant date	Between ±8 weeks after the implant anniversary date
Informed Consent	X						
Screening Committee Review	X						
Clinical Assessment	X		X	X	X	X	X
TPV Implant		X					
Echo	X 		X	X	X	X	X
Functional Cardiac Magnetic Resonance Imaging	X 			X 	X		To be completed at 2 & 5 Year Follow-Up
CT Cardiac Angiography	X 		X 				
Fluoroscopy		X		X	X	X	To be completed at 5 Year Follow-Up
Chest X-Ray			X				
SF-36	X 			X	X	X	X
Assessment of Adverse Event/ Device Deficiency	X	X	X	X	X	X	X

 Post-procedure care is carried out according to the standard care of the interventional cardiologist at his/her discretion.

 Clinical Assessment includes: at baseline – subject demographic, medical history, and medication assessment; at follow-up - medication assessment, review of adverse events, and device deficiencies.

 If an echo exam has been performed for routine diagnostic purposes prior to consenting, it can be used as the pre-implant echo exam, provided it was performed within 24 weeks prior to implant. The Principal Investigator must determine if the exam contains the protocol-required data and remains adequate for subject evaluation. If subject is screen failed, functional CMR imaging was used to satisfy the inclusion criteria, and pre-implant echo was not completed within window, a deviation is not required.

 If CMR imaging is contraindicated (e.g., subject has implantable cardiac rhythm device), no deviation will be required for MRI not performed.

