## 12. Statistical Design and Methods

The primary analysis for safety and effectiveness will be performed when the first 40 implanted subjects have completed their 6-month follow-up. A supplemental analysis will be performed when the 10 US implants of mTPV 25 cohort have completed their 1-month follow-up. Both cohorts will be pooled for additional analysis out to 5 years after the previously mentioned analyses are completed.

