### Device success out to 5 years

Device success is defined as:

- No device- or procedural-related mortality, with
- Original intended device in place, and
- No additional surgical or interventional procedures related to access or the device since completion of the original procedure (i.e., exit from the catheterization lab), and
- Intended performance of the device, as defined as:
  - Structural performance: No migration, embolization, detachment, major stent fracture, hemolysis, thrombosis, endocarditis, and
  - Hemodynamic performance: Relief of insufficiency (PR < moderate) without producing the opposite (mean RVOT gradient > 40 mmHg) as measured by continuous-wave Doppler echocardiography, and
- Absence of para-device complications, as defined by:
  - PVL ≥ moderate, or
  - Erosion, or
  - RVOT or PA rupture

---

 If a catheterization is performed for clinical purposes, the catheterization peak gradient measurement will supersede the continuous-wave Doppler echocardiography measurement and be used to support the outcome measure.

The analysis cohort for procedural success will be the attempted implant cohort. The endpoint will be described by Kaplan-Meier statistics. The loglog transformed two-sided 95% confidence interval using the Peto standard error at 6 months (183 days), 1 year (365 days), 2 years (730 days), 3 years (1095 days), 4 years (1460 days) and 5 years (1825 days) will be presented.

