## Procedural success at 30 days

Procedural success is defined as:

- Device success at 30 days, and
- None of the following device- or procedure-related serious adverse events:
  - Life-threatening major bleed
  - Major vascular or cardiac structural complications required unplanned reintervention or surgery
  - Stage 2 or 3 acute kidney injury (AKI) (includes new dialysis)
  - Pulmonary embolism
  - Severe heart failure (HF) or hypotension requiring IV inotrope, ultrafiltration, or mechanical circulatory support
  - Prolonged intubation >48 hours

The analysis cohort for procedural success will be the attempted implant cohort. The percentage of subjects with procedural success will be presented. If an element of the composite is missing and available elements meet the success criteria, the subject will be excluded from the analysis.

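### The 1-month mTPV 25 supplement does not score most of the device-failure items the plan already defines for 30 days, and its follow-up time is not fixed

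*SAP*

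**What the plan says.** SAP 7.8.2 and protocol 8.5 describe the mTPV 25 cohort at 1 month with three outcome sets.

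- The feasibility set asks for "deployment and correct positioning (including minor repositioning if needed) of the device", together with successful use and withdrawal of the delivery catheter and no related death.
- The hemodynamic set is a gradient limit only: "Mean RVOT gradient ≤ 40mmHg as measured by echocardiography". There is no regurgitation or paravalvular leak item.
- The safety set is "None of the following device- or procedure-related serious adverse events", and the three events it then names are a life-threatening bleed, "Major vascular or cardiac structural complications required unplanned reintervention or surgery", and, third, pulmonary embolism.

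The roll-in analysis at hospital discharge uses the same items (SAP 7.8.1, protocol 8.4).

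The plan also has a 30-day composite. Procedural success (protocol 12.3, SAP 7.11) begins with "Device success at 30 days, and" and adds freedom from six serious event types. Device success includes "Structural performance: No migration, embolization, detachment, major stent fracture, hemolysis, thrombosis, endocarditis, and", together with the other items compared below.

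On timing, protocol section 12 says: "A supplemental analysis will be performed when the 10 US implants of mTPV 25 cohort have completed their 1-month follow-up". SAP section 3 agrees. The Schedule of Events (protocol 8.1) allows the 1-month visit "Between 2 and 6 weeks after implant". Protocol 8.5 instead makes the analysis wait until subjects have been followed for 1 month. Neither document gives a day count or a data cut for this analysis.

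**The concern.** The list was built for hospital discharge. The time point was moved to 1 month, but nothing was added for failures that appear after the patient goes home. The imaging that would show them is scheduled: echo and fluoroscopy at 1 month for all implanted subjects, and functional CMR at 1 month for mTPV 25 subjects (unless contraindicated). Pulmonary regurgitation is the condition being treated, yet the 1-month set does not score it.

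This matters because no other analysis in the plan is specific to mTPV 25. The cohorts are pooled afterwards (protocol section 12, SAP section 3). The planned subgroups are age and gender only (SAP 7.9.3). Comparison of particular groups is made only if FDA asks (SAP 7.3). The PMA analysis of the primary efficacy endpoint excludes these subjects. Procedural success is due when all implanted subjects reach 6 months, and the first device-success estimate is at 183 days. Neither is scheduled with the supplement.

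**Working it through.** The plan gives no error rate, threshold or sample-size derivation for this analysis, so there is no figure to reproduce. The check has three parts.

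**1. Item comparison** (SAP 7.8.2 against procedural success and device success in SAP 7.11)

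| 30-day item | Named in the mTPV 25 set? |
|---|---|
| Related death | Yes (feasibility) |
| Mean gradient not above 40 mmHg | Yes (hemodynamics) |
| Life-threatening bleed; major vascular or cardiac structural complication needing reintervention or surgery; pulmonary embolism | Yes (safety profile) |
| Stage 2 or 3 AKI; severe heart failure or hypotension; intubation over 48 hours | No |
| Original device in place | No |
| No further device- or access-related procedure | No, except where the structural-complication item applies |
| Seven structural items (migration to endocarditis) | No (0 of 7) |
| Regurgitation below moderate | No |
| No PVL of moderate grade or worse, erosion, or rupture | No, except where the structural-complication item applies |

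Serious event types: 3 of 6 kept. The positioning item describes deployment, so it does not cover a later migration. A migration, major stent fracture, or regurgitation or leak of moderate grade or worse, found at follow-up with no reintervention and a gradient of 40 mmHg or less, fails none of the three sets.

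**2. Effect on the summary** (exact Clopper-Pearson intervals, number of failures over n)

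The upper limit for 0/n is 1 − 0.025^(1/n).

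- n = 10 (US implants): 0/10 gives 0 to 30.8%; 1/10 gives 0.3 to 44.5%; 2/10 gives 2.5 to 55.6%.
- n = 15 (if all five non-US implants are added): 0/15 gives 0 to 21.8%; 1/15 gives 0.2 to 31.9%.

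The counts of one and two are illustrations. The documents give no expected rate. Each unscored failure among 10 moves the proportion by 1/10 = 10 points.

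**3. Follow-up time**

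The window of 2 to 6 weeks is day 14 to day 42. A visit on day 14 leaves 30 − 14 = 16 of 30 days (53%) unobserved for that subject if data are cut at the visit. For the 10 US subjects over 30 days (300 person-days):

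- all cut at day 14: 10 × 14 = 140, or 47%;
- only the last subject cut at day 14: 9 × 30 + 14 = 284, or 95%.

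The chance of seeing at least one event, for an assumed 30-day risk p (not in the documents) with events spread evenly over 30 days, is:

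| p | Full 30 days: 1 − (1 − p)^10 | Last subject only at day 14: 1 − (1 − p)^9 × (1 − 14p/30) | All at day 14: 1 − (1 − 14p/30)^10 |
|---|---|---|---|
| 5% | 40% | 38% | 21% |
| 10% | 65% | 63% | 38% |
| 20% | 89% | 88% | 62% |

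The timing effect therefore runs from negligible to large, depending on a cut-off rule that the plan does not state.

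**The case against.** The supplement is a short, prespecified feasibility summary with no pass mark, so no decision rule turns on it. Related serious events and deaths are summarised study-wide from CEC data (SAP 7.10), the DMC reviews all serious events and deaths, and procedural and device success are analysed later. The SAP also expects further analyses beyond the plan. All of this is correct, and it limits the point to what this supplement reports at 1 month. It does not close the gap: SAP 7.10 promises no separate mTPV 25 table, and a fracture, migration or leak seen only on imaging need not be a serious adverse event.

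Three stronger readings are tempting, and the documents do not support them.

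- A reader might infer that every device-success item is dropped. Related death and gradient are kept.
- A reader might infer that an explanted valve counts as a clean result. Removal for a major structural complication may fall under the second listed event. Explant for another reason, such as endocarditis or thrombosis, may not. The event definitions in protocol Appendix II are redacted, so this cannot be settled.
- A reader might infer that the look happens at day 14. That is only the earliest permitted visit. The trigger waits for all ten US implants, subjects treated earlier may have longer follow-up, adverse events are recorded continuously until study exit, and protocol 8.5 speaks of a full month.

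The readable text also does not say what was changed in the modified valve, so it cannot be argued that the missing items are the ones the change affects.

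**Conclusion.** The point holds within limits. The supplement omits three of the six serious event types and the device-success items other than related death and gradient, although the plan defines all of them for 30 days and schedules the 1-month imaging that would show migration, fracture or leak. As worded, it cannot show as a failure a valve that migrates, fractures or leaks without reintervention and with an acceptable gradient. Among 10 subjects, one such case separates 0/10 from 1/10, and the upper limit on the failure rate moves from 30.8% to 44.5%. A zero here would be a zero-event description, not a criterion met.

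The trigger wording is inconsistent between protocol 8.5 and protocol section 12 with SAP section 3. The loss of follow-up is 5% of person-days if only the last subject is cut at day 14, and 53% if all are. Both figures assume that data are cut at the visit, which the documents neither state nor exclude.

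**What to change.** In SAP 7.8.2 and protocol 8.5:

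1. Report procedural success at 30 days for the mTPV 25 cohort as already defined, with each component shown. It contains device success, so device success need not be added separately.
2. List CEC-adjudicated device- or procedure-related serious adverse events through day 30.
3. Reconcile the trigger in protocol 8.5 with that in protocol section 12 and SAP section 3. State a data cut no earlier than day 30 after implant for every counted subject.
4. State how an explanted subject is counted. Under SAP 7.4, a subject with no 1-month echo would otherwise drop out of the hemodynamic result.

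The cost is wording in two documents, one or two tables, and a delay of the cut of at most about 16 days (30 − 14). No new visit or test is needed, and the analysis remains descriptive with no threshold.
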